## Methods

We performed a single-site, prospective, parallel group, un-blinded randomized clinical trial which enrolled a convenience sample of patients aged 2-20 years with previously diagnosed asthma presenting to a single emergency department with a mild to moderate exacerbation of asthma. The hospital's institutional review board approved the study and informed consent was obtained from eligible patients' legal guardians or adult patients (18-20 years age). In addition, patients 7 to 17 years of age provided written ascent.

### Study Setting and Participants:

Children aged 2 to 20 years with a known history of asthma who presented to the Emergency Department at Women and Children's Hospital of Buffalo/Oishei Children's Hospital between April 2015 and March 2018 with an acute exacerbation of mild or moderate asthma were eligible for the study. Asthma severity was defined by Pediatric Asthma Scores[2, 12] (PAS). Mild asthma is defined as: PAS of 5 to 7; Moderate asthma is defined as: PAS of 8 to 11; Severe asthma is defined as: PAS of 12 or more. History of asthma is defined by physician diagnosis of at least one prior episode of wheezing which responded to beta agonists. Patients were excluded from the study if they had signs of severe asthma exacerbation (PAS of 12 or more), had used oral steroids in the last 2 weeks, had chronic lung disease (e.g., cystic fibrosis), had been given parenteral steroids, or if they vomited two doses of oral steroids in emergency department.

Research assistants screened asthma patients through the electronic medical record between the hours of 8 a.m. and 11 p.m. 7 days a week. Patients were approached sequentially based on registration time. If a patient appeared to meet study criteria, his/her ED treating physician was approached by the research assistant for identifying patient's eligibility. If a patient was fully eligible, the legal guardian and/or patient were approached for consent.

### Study Protocol:

Block randomization was used to generate a list to be used for subject assignment with a 1:1 ratio of allocation to the single dose group and the two dose group. Demographic information such as age, gender, race, duration of asthma symptoms, number of previous hospitalizations, and current medication was collected. Pertinent exam findings such as patient's vital signs, pulse oximetry, and PAS were also collected along with medications given in the ED.

Group 1 was given 0.6mg/kg (max 16mg) of dexamethasone orally in the emergency department. Group 2 was given the same dose in the emergency department, and then a prescription for a second dose was sent to their pharmacy to be filled and administered at home 24 hours later. We worked with a nearby 24-hour pharmacy to ensure medication availability; however, pharmacy preference was left up to the family. Both groups received asthma treatment following a standardized asthma care path.

All patients were contacted by phone by a research assistant on the 6th day following the emergency department visit. Research assistants were not completely blinded during the study. They were initially blinded to the study group at the start of the phone interviews; however, during the course of the

interview they did ask if the prescription for the second dose of dexamethasone was filled and if the medication was given to the patient. Information collected during the phone interview included additional visits to medical providers (ED, primary care or urgent care) for continued asthma symptoms, information was collected on the reason for visit, whether symptoms continued or worsened, and if additional treatment was needed (scheduled visits and unrelated visits were excluded). School days missed due to asthma exacerbation; length of time symptoms persisted; compliance with the recommended steroid regimen; and any vomiting, side effects or medication administration problems caused by the steroids was also collected.

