#### Analytic Plan:

Descriptive characteristics were computed for all patients combined and separately by dexamethasone group assignment. Categorical variables were reported as proportions in percentage, and continuous level variables as means and standard deviations. Separate independent t-tests were used to assess differences by group for post-discharge outcomes of interest including days for symptoms to resolve. Separate binary logistic regression adjusting for age, gender and severity of exacerbation were conducted to assess group differences in post-discharge outcomes including patients who had a return visit for unresolved asthma symptoms (ED, primary care or urgent care), days to symptom resolution, any missed school days between discharge and follow-up, rates of vomiting, and side-effects (changes in appetite, insomnia, mood swings); odds ratios with 95% confidence intervals were reported. Similar analyses were conducted to compare events and side effects between Groups 1 and 2 by asthma severity, using an intention-to-treat approach. Based on our clinical experience, we based our a-priori sample size calculation on an estimated non-inferiority limit of 11% and a rate of 12% return for asthma for each group. With a power of 80% and alpha of 0.05, a minimum sample size of 216 (108 subjects per group) was determined. All statistical tests were two-tailed, and analyses conducted with SYSTAT 13 (SYSTAT Software, 2004).

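### The second-dose question in the day-6 call generally reveals the arm, and no masking is described for the exclusion of scheduled or unrelated visits: a possible bias, not a shown one, and cheap to reduce

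*Combined protocol and SAP*

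**What the plan says.** The Methods section describes a "parallel group, un-blinded randomized clinical trial". Under Study Protocol, both groups are dosed in the emergency department. In Group 2 only, "a prescription for a second dose was sent to their pharmacy" for use at home.

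A research assistant phones every family on day 6. The section admits that these callers were not fully blinded: "They were initially blinded to the study group at the start of the phone interviews". It then says of a later point in the call: "interview they did ask if the prescription for the second dose of dexamethasone was filled and if the medication was given to the patient".

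The call also covers further visits to medical providers. For these, "information was collected on the reason for visit, whether symptoms continued or worsened, and if additional treatment was needed", and a parenthesis adds that "scheduled visits and unrelated visits were excluded". Missed school, duration of symptoms, compliance, vomiting and other side effects come from the same call.

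The Analytic Plan names a return visit for unresolved asthma symptoms among the outcomes compared by logistic regression. It bases the sample size on a 12% return rate in each group and a non-inferiority limit of 11%.

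**The concern.** A Group 1 family has no second prescription to fill, so the answer to the second-dose question will usually tell the caller which arm the child is in. It will not always do so, because a Group 2 family that never filled the prescription may also answer no.

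Whether a primary-care visit a few days after an exacerbation was scheduled, unrelated, or due to asthma that had not resolved is a matter of judgement. If that judgement is made by someone who knows the arm, it can be applied differently in the two groups. The documents do not say who made it, when, or whether group was hidden.

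The outcome at stake is the one that drives the sample size. About 26 qualifying visits are expected (12% of 216), so a handful of decisions could matter.

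**Working it through.** **Order of events in the text.** The Study Protocol gives initial blinding, then the second-dose question at an unstated point in the call, then the list of what was collected. In that list, return visits stand before compliance. Nothing says that the list follows the order of the questions, or whether exclusions were applied during the call or afterwards. The text leaves the sequence open.

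**The plan's own figure.** Inputs from the Analytic Plan: 12% in each group, limit 11 points, power 80%, alpha 0.05.

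- One-sided 5%: n per group = 2 × 0.12 × 0.88 × (1.645 + 0.8416)² / 0.11² = 107.9, so 108 per group and 216 in total. This matches the plan.
- One-sided 2.5%, which corresponds to a two-sided 95% interval, gives 137 per group and does not match.

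The plan does not state the sidedness of this calculation, and it says that all tests were two-tailed. Both bases are therefore shown below.

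**How many visits matter.** One visit is 1/108 = 0.93 points. The upper limit is p1 − p2 + z × √(p1q1/108 + p2q2/108), where Group 1 is the single dose and Group 2 has 13 events (about 12%).

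| Group 1 events | One-sided 95% (z = 1.645) | Two-sided 95% (z = 1.96) |
|---|---|---|
| 15 | 9.4 points | 10.8 points |
| 16 | 10.4 points | 11.9 points |
| 17 | 11.4 points | – |

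The limit first exceeds 11 points at 17 events on the one-sided basis and at 16 on the two-sided basis. Three or four visits separate equal counts from missing the margin.

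**What selective loss of visits could do (illustration).** The chance of meeting the margin is Φ((0.11 − (p1 − p2))/SE − z), with SE = √(p1q1/108 + p2q2/108). The documents give no misclassification rate. The loss fractions of 10% and 20% are assumptions, and the direction of any loss is unknown.

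(a) True rates 23% versus 12%, a difference equal to the margin. Group 1 expects 0.23 × 108 = 24.8 events, so 10% or 20% is 2.5 or 5.0 visits.

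| Observed rates | One-sided 5% | Two-sided 95% limit |
|---|---|---|
| 23.0% vs 12% (no loss) | 5.0% | 2.5% |
| 20.7% vs 12% (10% lost in Group 1) | 11.8% | 6.7% |
| 18.4% vs 12% (20% lost in Group 1) | 24.2% | 15.5% |
| 20.7% vs 10.8% (10% lost in both) | 7.8% | 4.1% |
| 18.4% vs 9.6% (20% lost in both) | 12.0% | 6.8% |

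The last two rows matter for reading the others. Equal loss in both arms also raises the error, and masked classification would not prevent that part.

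(b) True rates 12% in both groups, with the loss in Group 2. Group 2 expects 0.12 × 108 = 13.0 events, so 10% or 20% is 1.3 or 2.6 visits. The chance of meeting the margin falls from 80% to 73% or 65% (one-sided 5%), or from 70% to 62% or 53% (two-sided 95% limit).

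**On the odds-ratio scale the plan reports.** Take 12% in both groups, single versus two doses, unadjusted. Losing 10% or 20% of Group 2 events moves the odds ratio from 1.00 to (0.12/0.88)/(0.108/0.892) = 1.13 or (0.12/0.88)/(0.096/0.904) = 1.28. The same losses in Group 1 give the reciprocals, 0.89 and 0.78.

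**The case against.** The strongest reply is that the documents disclose the problem and may already limit it. The trial is called un-blinded, the callers' partial unblinding is stated openly, and the callers began each call blinded. If return visits were asked about and classified before the second-dose question, as the order of the list might suggest, they were recorded before the arm was known. This stands as far as it goes: it is a partial safeguard, though the text does not confirm that order.

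A second reply is that the remedy may have little to work on. The exclusion appears in a parenthesis inside the description of the call, so scheduled or unrelated visits may have been filtered out on the phone and never recorded. Re-reading could then remove counted visits but not restore dropped ones. This also stands, and it makes the remedy conditional. In addition, the recruitment period is given as "between April 2015 and March 2018", and nothing indicates that calls remain to be made.

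A third reply is that the figures are hypothetical. Scenario (a) puts the true difference exactly at the margin and all the loss in one arm, and the Analytic Plan uses the margin only for the sample size. That is correct. The figures show sensitivity to a few visits and nothing more.

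A reader might go further and infer that asthma return visits were discarded without any blinding, or that callers who knew the arm tilted the result. The documents support neither. The visits left out were the scheduled and unrelated ones, callers were blinded at the start, and the text does not show that any visit was classified with the arm known.

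**Conclusion.** The point holds as an inexpensive improvement to how outcomes are recorded and reported. Three things are established: the second-dose question generally reveals the arm, no masking is described for the step that removed scheduled or unrelated visits, and the question order is not given. Whether any bias arose, and in which direction, cannot be told from the documents.

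The practical weight comes from the small number of events. The margin comparison turns on three or four visits, and the error rates in scenario (a) more than double with a 10% one-sided loss on either basis. That rests on 108 analysed per group, the normal approximation, and loss fractions that are assumed. The required sample size of 216 is not affected.

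**What to change.** - **Calls.** Record and lock return visits with their reasons, symptom duration, missed school, vomiting and side effects before the prescription, administration and compliance questions. If all calls are complete, report the order that was used.
- **Classification.** Where visit reasons were recorded, an existing team member, with the group code and any mention of the second dose hidden, classifies every reported visit as scheduled, unrelated or qualifying. The basis is the recorded reason, symptom course and additional treatment. Include excluded visits if their records exist.
- **Reporting.** State who decided the exclusions, when, and whether group was hidden. If excluded visits were not kept, or the exclusion was applied during the call, give this as a limitation.

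The cost is re-reading a few dozen records: about 26 qualifying visits (0.12 × 216) plus whatever excluded visits were kept. No new calls or patients are needed for the re-reading. It cannot remove bias already in answers recorded after the arm was known, nor reporting bias from families who know their group.

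### Vomiting and side effects are compared over a period that includes the shared first 24 hours, with no onset day listed, so a finding of no difference would say little about the second dose

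*Combined protocol and SAP*

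**What the plan says.** Under Study Protocol, "Group 2 was given the same dose in the emergency department" as Group 1, followed by a prescription for a second dose "to be filled and administered at home 24 hours later". Other care is common to the arms: "Both groups received asthma treatment following a standardized asthma care path". By design, nothing differs between the groups until about 24 hours after the ED dose.

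Follow-up is one interview, with patients "contacted by phone by a research assistant on the 6th day following the emergency department visit". On tolerability, the items listed end with "any vomiting, side effects or medication administration problems caused by the steroids was also collected". Neither the day of onset nor the dose that preceded the event is listed. The interview also asks whether the second dose was filled and given. The assistants start the call unaware of the group and may learn it from that question.

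The Analytic Plan uses adjusted logistic regression to "assess group differences in post-discharge outcomes including patients who had a return visit for unresolved asthma symptoms", and the same list includes "rates of vomiting, and side-effects (changes in appetite, insomnia, mood swings". Results are reported as odds ratios with 95% confidence intervals. No analysis begins at the point where the arms diverge.

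**The concern.** The tolerability question in a one-dose versus two-dose trial is what the second dose adds. An any-versus-none outcome over the whole period answers it only indirectly. A child who vomits or sleeps badly on the evening of the ED visit counts as an event, whichever group the child is in. If that child is in Group 2 and reacts again to the home dose, the second reaction changes nothing.

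Randomisation makes these first-day events equally likely in both arms, so they do not bias the test towards a false difference. They do raise both event rates by a common amount. That moves the odds ratio towards 1 and adds variance. A report of no difference in vomiting or side effects could then be read as evidence that the second dose is well tolerated, when the comparison had little chance of showing otherwise.

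**Working it through.** **Inputs from the documents.** 108 per group, two-tailed tests, divergence at 24 hours, one call on day 6. For returns, 12% in each group and a limit of 11%.

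**The plan's own figure.** For non-inferiority on a risk difference at one-sided 0.05 and 80% power, n per group = (1.645 + 0.842)² × 2 × 0.12 × 0.88 / 0.11² = 107.9, so 108 and 216 in total. This matches the stated size. It also shows that the trial was sized on returns, and that the limit behaves as a risk difference.

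**Assumed inputs.** The documents give no vomiting or side-effect rates. Let s be the risk of an event before 24 hours (equal in both arms), b the later background risk in Group 1, and d the points added by the second dose.

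**Formulas.** The whole-period risk is s + (1 − s)b in Group 1 and s + (1 − s)(b + d) in Group 2. The whole-period risk difference is therefore (1 − s)d. The after-24-hour risks are b and b + d. Power is by exact binomial enumeration of the two-sided 5% Pearson test, unadjusted, with 108 per group in both comparisons.

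**Example, s = 5%, b = 1%, d = 8 points.** Group 1: 0.05 + 0.95 × 0.01 = 5.95%. Group 2: 0.05 + 0.95 × 0.09 = 13.55%. The difference is 7.6 points. The odds ratio is (0.1355/0.8645)/(0.0595/0.9405) = 2.48. After 24 hours it is (0.09/0.91)/(0.01/0.99) = 9.79.

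| Shared s | Late background b | Added d | Whole-period OR | Power | After-24-h OR | Power |
|---|---|---|---|---|---|---|
| 5% | 1% | 8 | 2.48 | 49% | 9.79 | 82% |
| 5% | 5% | 8 | 1.94 | 38% | 2.84 | 56% |
| 5% | 10% | 8 | 1.67 | 30% | 1.98 | 40% |
| 10% | 1% | 5 | 1.49 | 17% | 6.32 | 52% |
| 5% | 10% | 5 | 1.41 | 15% | 1.59 | 20% |

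The direction is the same in every row. The gain from separating the periods is large when late background events are rare and modest when they are common. The risk difference is far steadier than the odds ratio: with 5% shared events, 8 points becomes 7.6.

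**Returns.** Take a total of 12% in the two-dose group and a true after-24-hour excess of 11 points in the single-dose group. If half of the 12% occur early, s = 6% and the whole-period difference is 0.94 × 11 = 10.3 points. The chance of wrongly declaring non-inferiority at one-sided 0.05 rises from 5.0% to 6.5%. If a quarter occur early, it is 5.7%.

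**Recall error.** Suppose the second dose has no effect, with s = 10% and b = 1%. If Group 2 families place 20% of early events after 24 hours and Group 1 families place none there, the apparent late risk in Group 2 is 0.01 + 0.20 × 0.10 = 3%. The odds ratio is (0.03/0.97)/(0.01/0.99) = 3.06, and the test rejects about 16% of the time.

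**The case against.** The strongest reply is that the whole-period comparison is a proper one. It contrasts two prescribed regimens from the ED visit onwards, and a family's total burden of vomiting and side effects under each is a fair question. It does not depend on when an event is said to have started. An after-24-hour comparison does, and in an un-blinded trial Group 2 families have a home dose to which they can attach symptoms. The recall calculation shows that this could produce a false signal. This stands, and it is why the later comparison should be supportive only.

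The large odds ratios after 24 hours also depend on an assumed 1% background. At 5% or 10%, power after 24 hours stays below 60%, so the new table would often be inconclusive too. Part of the problem is simply that the sample size was set on returns. This also stands.

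The interview form is not shown, and the items are introduced as what the call included. Onset may have been recorded. The text supports only the statement that it is not listed.

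A reader might infer something stronger: that shared events hide any effect of the second dose, on returns as well as on tolerability. The documents do not support that. Early events dilute the contrast without cancelling it, the risk difference shrinks only by the factor 1 − s, and the 11-point limit on returns is hardly affected.

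**Conclusion.** The point holds for vomiting and side effects, as dilution. The arms are treated alike for 24 hours, the analysed period includes the part of that time after discharge, and neither the listed items nor the analysis separates the two periods. A finding of no difference would be weak evidence that the second dose is well tolerated.

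The size is uncertain. Under 5% shared events and 8 added points, the power given up ranges from 33 percentage points (82% − 49%) at a 1% late background to 10 points (40% − 30%) at 10%. It shrinks further if early events are rare. These figures assume that early and late events are independent, that early risk is equal in the two arms, and that onset is dated correctly. Late effects of the first dose would still occur after 24 hours in both groups and are part of the background.

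The sample size of 216 and the return-visit comparison are essentially unaffected. This is a cheap improvement to secondary outcomes and leaves the main result as it is.

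**What to change.** - In the day-6 call, record for each vomiting episode and side effect whether it began before or after 24 hours from the ED dose. Ask it identically in both groups, and before the questions about the second dose, while the assistant is still unaware of the group.
- Keep the whole-period comparison as main. Report it as a risk difference with a 95% confidence interval as well as the odds ratio.
- Add a supportive comparison of events with onset after 24 hours, in all patients as randomised. Use the same clock in both groups, whether or not the second dose was taken.
- Leave the return-visit analysis as it is.

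The cost is one question per event in an existing call and one more table. The drawback is six-day recall, which may misplace onset differently by group. The after-24-hour result should be labelled supportive and this limitation stated beside it. The document is written in the past tense. If collection is closed and onset was not recorded, the risk difference with its interval can still be reported, with a sentence saying that first-dose and second-dose events could not be separated.

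### Harms in the day-6 call are described as steroid-caused in an un-blinded trial where only one arm has a home dose, so attribution may differ by arm and distort the tolerability comparison

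*Combined protocol and SAP*

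**What the plan says.** All references are to the combined protocol and SAP.

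- **Methods** describes a "parallel group, un-blinded randomized clinical trial".
- **Study Protocol** gives both groups dexamethasone in the emergency department. For Group 2 alone, "a prescription for a second dose was sent to their pharmacy to be filled and administered at home 24 hours later". No placebo or sham second dose is described for Group 1.
- **Study Protocol**, on follow-up: "All patients were contacted by phone by a research assistant on the 6th day following the emergency department visit". It adds that "Research assistants were not completely blinded during the study": they start the call unaware of the group, then ask whether the second dose was filled and given. The order of the questions is not stated.
- **Study Protocol**, on harms: "any vomiting, side effects or medication administration problems caused by the steroids was also collected". It does not say who judges cause, or whether events not attributed to the steroid were also recorded.
- **Analytic Plan** lists among the compared outcomes "rates of vomiting, and side-effects (changes in appetite, insomnia, mood swings); odds ratios with 95% confidence intervals were reported". No causal condition appears there.

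**The concern.** The two sections describe the harm outcome differently. What is collected carries a causal condition; what is analysed does not.

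The condition matters because vomiting, appetite change, insomnia and mood swings are non-specific and can occur in any child recovering from an acute illness. If such a symptom counts only when someone links it to the steroid, the recorded rate depends on willingness to make that link as well as on how often the symptom occurs. In an un-blinded trial that willingness can differ by arm. A Group 2 family that gave a steroid at home has a second, self-administered dose to point to; a Group 1 family has only the dose given in the emergency department.

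Tolerability is a natural argument for a single dose. A difference in attribution could produce or enlarge an apparent advantage. Adjustment for age, gender and severity, or analysis by intention to treat, would not remove it, because the error arises when the event is recorded. Randomisation already supports a causal comparison of all-cause events, so the comparison does not need a judgement of cause for each event.

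**Working it through.** **The plan's own figure.** The documents give no expected or observed rate for vomiting or side effects, and no attribution shares, so there is nothing to reproduce on this point. The planned 108 per group comes from the return-visit outcome and is used below only as a group size.

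**The two descriptions side by side.**

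1. In the Study Protocol sentence the causal phrase closes a list of three: vomiting, side effects, administration problems. It may govern all three or only the last.
2. On either reading, the term side effects already implies an effect of the drug. Attribution is therefore built into that item, and only vomiting is truly ambiguous.
3. The Analytic Plan names three symptoms under side effects, which could reflect a fixed list asked of everyone. It does not say so.
4. The only stated post-discharge source is a phone interview with the family or patient, so they are the likely judges of cause. This is an inference.

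**Illustration of the mechanism (all rates and shares assumed).**

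- Recorded rate = true rate × share attributed to the steroid.
- Odds ratio, two doses v one = [r2/(1 − r2)] / [r1/(1 − r1)], where r1 and r2 are the recorded rates in Groups 1 and 2.
- Chance that an unadjusted two-sided 5% test falsely favours one dose, with n = 108 per group: Φ{[(r2 − r1) − 1.96·√(2p(1 − p)/n)] / √([r1(1 − r1) + r2(1 − r2)]/n)}, where p = (r1 + r2)/2.

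True rate 20% in both arms, so the true odds ratio is 1.00:

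| Attributed, Group 1 v Group 2 | Recorded rates | Odds ratio, two v one | Chance of falsely favouring one dose |
|---|---|---|---|
| 50% v 50% | 10% v 10% | 1.00 | 2.5% (nominal) |
| 50% v 60% | 10% v 12% | 1.23 | 7% |
| 60% v 80% | 12% v 16% | 1.40 | 13% |
| 50% v 75% | 10% v 15% | 1.59 | 20% |
| 50% v 90% | 10% v 18% | 1.98 | 39% |

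For the third row: (0.16/0.84) / (0.12/0.88) = 0.1905/0.1364 = 1.40.

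**Sensitivity to the true rate.** For the 60% v 80% and 50% v 90% pairs, true rates of 10% to 30% give odds ratios from 1.36 to 2.10. The ends are (0.08/0.92)/(0.06/0.94) = 1.36 and (0.27/0.73)/(0.15/0.85) = 2.10.

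**Sensitivity to direction.** If Group 1 families attributed more (80% v 60%), the recorded rates would be 16% v 12% and the odds ratio 1/1.40 = 0.72, favouring two doses.

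**The case against.** The strongest reply is that the text does not establish how the question was asked. One sentence in the Study Protocol summarises what was collected; it is not the call script. The causal phrase may attach only to administration problems. The Analytic Plan, which defines what is compared, has no such phrase, and its named symptoms are consistent with a fixed list. This stands as a reason for caution. It does not remove the point, because side effects implies attribution on either reading and the two sections do not match as written.

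A second reply concerns direction. Both groups received dexamethasone, so a Group 1 family also has a steroid to name. By the day-6 call the two doses are of similar age, about 6 days and about 5. Group 2 families who did not give the second dose have no home dose to blame, which dilutes any effect under intention to treat. An excess in Group 2 could also be a genuine effect of the extra dose. All of this stands.

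Third, the attribution shares are invented and cannot serve as evidence of bias. That is also correct: they show only how the odds ratio responds.

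A reader might infer more than the documents support: that events were recorded only when an un-blinded family blamed the steroid, that a single dose therefore looks better tolerated than it is, and that asking about cause can do nothing but bias the comparison. The documents name no judge of cause, do not say that unattributed events were discarded, and give no evidence of which arm attributes more. Equal attribution lowers both rates without creating a difference when there is none. A causal condition also keeps out background symptoms that would blur a real effect.

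**Conclusion.** The concern holds in limited form. The plan describes harms with a causal condition where they are collected and without one where they are analysed. In an un-blinded trial with a home dose in one arm only, that leaves an avoidable route for differential attribution. If attribution is higher in Group 2, one dose may look better tolerated relative to two doses; this direction is plausible, not established.

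The size cannot be fixed from the documents. The illustration's 1.40 assumes no true difference, a common true rate of 20% and attribution of 60% v 80%; it vanishes if attribution is equal. The chances of a false finding further assume 108 analysed per group and an unadjusted test, whereas the plan uses adjusted logistic regression.

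The point touches only the vomiting and side-effect comparisons. The return-visit outcome and the sample size built on it are unaffected.

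**What to change.** **In the call.** Ask vomiting, appetite change, insomnia and mood swings each as a yes/no item covering the time since the ED visit, whatever the family thinks the cause was. Use identical wording in both arms, and put these items before the questions about filling and giving the second dose, which reveal the group to the interviewer.

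**In the analysis.** Use these all-cause events for the Analytic Plan's odds ratios. Keep perceived cause as a descriptive item, and state who judged it.

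**If calls are complete.** The text is in the past tense and gives an enrolment period ending in March 2018, so this case is likely. State how the items were asked and whether unattributed events were recorded. If they were, compare all-cause events. If only attributed events were recorded, report the harm comparison as open to differential attribution.

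**Cost.** A few lines of call script and one outcome definition, with no change to the sample size. Background symptoms will raise the rates in both arms and somewhat dilute a genuine second-dose effect. Un-blinded families may still report differently by arm, so the change reduces the problem without removing it.
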